### 5.6.1 Proportion of subjects who achieve a 3-point or greater increase from baseline in HFSME at 15 months

#### 5.6.1.1 Final analysis

##### *Main analysis*

The multiple imputation datasets produced for the analysis of the primary endpoint will be utilized. If a subject terminates the study prior to the 15-month assessment due to treatment failure or death, then the imputed value from the multiple imputation will be ignored and the subject will be considered a non-responder. Any subject in the ITT Set who has an increase from baseline HFMSE score of 3 or more points at Month 15 will be defined as a responder; otherwise, a subject will be considered a non-responder.

Treatment groups will be compared using logistic regression adjusting for each subject's age at screening and baseline HFSME score.

##### *Sensitivity analysis*

Four sensitivity analyses will be performed. In the first, the main analysis described above will be performed on the PPS.

In the second, performed on the ITT Set without any imputation, any subject who has an increase from baseline in HFMSE score of 3 or more points at Month 15 will be defined as a responder. If this was not achieved or the Month 15 value is missing, a subject will be defined as a non-responder.

In the third, performed on the ITT Set without any imputation, if a subject terminates the study prior to the 15-month assessment due to treatment failure or death, then the subject will be considered as a non-responder, if the subject has missing Month 15 due to any other reason, he/she will not be included in the analysis.

In the fourth sensitivity analysis, only the subset of subjects in the ITT Set who have non-missing values at 15 months will be analyzed. Any subject who has an increase from baseline in HFMSE of 3 or more points at Month 15 will be defined as a responder; otherwise, he/she will be considered a non-responder.

Treatment groups will be compared using logistic regression adjusting for each subject's age at screening and baseline score.

### 5.6.1.2 Summary of analyses

#### Summary of analyses for the secondary endpoint, proportion of subjects who achieve a 3-point or greater increase from baseline in HFMSE at 15 months

Analysis Method	Final Analysis - Population: further notes
Main analysis	
Logistic regression adjusting for each subject's age at screening and baseline HFSME score. Subjects who terminate the study prior to the 15-month assessment due to treatment failure or death will be considered as a non-responder	ITT; multiple imputation used to impute missing 15-month values
Sensitivity analyses	
Logistic regression adjusting for each subject's age at screening and baseline HFSME score. Subjects who terminate the study prior to the 15-month assessment due to treatment failure or death will be considered as a non-responder	PPS; multiple imputation used to impute missing 15-month values
Logistic regression adjusting for each subject's age at screening and baseline HFSME score. Subject with an increase of 3 or more points will be considered a responder, else he/she will be considered a non-responder.	ITT, no imputation
Logistic regression adjusting for each subject's age at screening and baseline HFSME score. Subjects who terminate the study prior to the 15-month assessment due to treatment failure or death will be considered non-responders	ITT, subjects with missing Month 15 not deemed due to treatment failure or death are excluded.
Logistic regression adjusting for each subject's age at screening and baseline HFSME score.	ITT, with non-missing 15-month values

### 5.6.2 Proportion of subjects who achieve any new motor milestones at 15 months

The WHO motor milestones are a set of six milestones in motor development, all of which would be expected to be attained by age 24 months in healthy children. The individual milestones are:

- Sitting without support
- Standing with assistance

- Hands and knees crawling
- Walking with assistance
- Standing alone
- Walking alone

Per the study inclusion criterion number 5, subjects would be expected to all have achieved and maintained at baseline the milestone ‘Sitting without support’ but none would have achieved the milestone of ‘Walking alone’. The motor milestones are assessed at seven study visits using the WHO motor milestone criteria [WHO Multicentre Growth Reference Study Group 2006]. As part of the assessment, the examiner records an overall rating of the subject’s emotional state and then for each milestone one of the following four classifications:

- No (inability) – Child tried but failed to perform the milestone
- No (refusal) – Child refused to perform despite being calm and alert
- Yes – Child was able to perform the milestone
- Unable to test – Could not be tested because of irritability, drowsiness or sickness

#### *Imputation for motor milestones*

If for a milestone either ‘No (refusal)’ or ‘Unable to test’ are observed at a visit then the result will be first set to missing. Imputation will be performed for missing data considering each milestone separately using the following rules for scheduled visits.

For baseline, the closest non-missing milestone prior to or at first dose will be selected. If the motor milestone is still missing then the missing value will be imputed as the median of the non-missing values of the stratum to which the subject belongs to: Age at screening < 6 years or Age at screening  $\geq$  6 years. In the event that the median at baseline is 0.5 then then the missing value will be imputed as 1. If, for the subject with a missing value at a particular visit the corresponding visit is flanked by visits with non-missing milestones, the missing value will be imputed by using the worst result from the flanking visits. Otherwise, if the imputation is the last visit, the missing value will be imputed as the lowest value observed across all subjects who have a non-missing value at this visit within the stratum: Age at screening < 6 years or Age at screening  $\geq$  6 years within the treatment group. Of note, only observed data will be utilized for imputation purposes and in a situation where unscheduled visit data is available these values will be utilized if these flank a missing visit. Missing motor milestone items will be imputed first prior to any analysis.

##### **5.6.2.1 Final analysis**

###### *Main analysis*

Treatment groups will be compared using logistic regression adjusting for each subject’s age at screening and baseline number of milestones. Missing data will be handled as described in Section 5.6.2. If a subject terminates the study prior to the 15-month assessment due to treatment failure or death then any imputed value will be ignored and the subject will be considered a non-responder. For the remaining subjects, the 15-month milestone data will be

assessed and if the baseline milestones achieved are still maintained at Month 15 and the subject has achieved at least one new milestone, he/she will be considered a responder.

Should the number of responders be less than 5 in either group, Fisher's exact test will be used instead. If Fisher's exact test is used, the unconditional confidence interval for the difference in response rates will be provided (Santner and Snell 1980).

#### *Sensitivity analysis*

Several sensitivity analyses will be performed. In the first, the analysis described above will be performed on the PPS. In the second, the analysis will be performed on the ITT Set and any subject who is missing all six milestone assessments at Month 15 will be considered a non-responder. If 5 or fewer milestone assessments are missing at Month 15 then any missing individual milestones will be set to 'Not (Inability)' and for each subject the Month 15 milestone data will then be assessed compared to baseline to determine response as in the main analysis. In the third sensitivity analysis, performed on the ITT Set, any subject who is missing the Month 15 visit due to treatment failure or death will be considered to be a non-responder. Any subject who is missing all Month 15 milestone assessments for any other reason will be excluded from the analysis; otherwise, the analytical method will be the same as that for the previous analysis.

In the fourth sensitivity analysis, only the subset of subjects in the ITT Set who have non-missing values for all six milestones at 15 months will be analyzed. If the baseline milestones achieved are still maintained at Month 15 and the subject has achieved at least one new milestone they will be considered as a responder. Treatment groups will be compared using logistic regression adjusting for each subject's age at screening and baseline score.

#### *Exploratory analysis*

Several additional analyses will be performed on the ITT Set (without any imputation) to further explore the consistency in achievement and maintenance of motor milestones during the course of the study. In the first analysis, the proportion of subjects who achieve at least one new milestone compared to baseline and then maintain this milestone at successive visits will be assessed. In order to be assessed as a responder, subjects would need to have completed the study and the following will also apply:

- Milestones achieved at baseline are maintained across all study visits
- The visit at which a subject first achieves at least one new milestone will be considered. At least one of any new milestones achieved at this visit will then need to be maintained at subsequent visits
- At least two successive visits are required. Thus, the first new milestone will need to be achieved at the latest by Month 12 in order to allow confirmation at Month 15

In the second analysis, the proportion of subjects who achieve new milestones compared to baseline and maintain these milestones at successive visits will be assessed. The definition will be similar to the first analysis but whenever a subject achieves any new milestone, this milestone will need to be maintained to Month 15. Having first achieved any new milestone

compared to baseline, if a subject is unable to demonstrate maintenance of the milestone(s) at future visits, he/she will be defined as a non-responder.

The proportion of subjects defined as responders under each definition will be analyzed by logistic regression adjusting for the subject's age at screening and baseline number of milestones. In addition, for each of these analyses, the number of visits at which a subject was judged to maintain the milestone as a responder will be summarized using counts and percentages. In this summary, non-responders will be presented as zero and 2, 3, 4 and 5 will be possible counts for responders.

### 5.6.2.2 Summary of analyses

#### Summary of analyses for the secondary endpoint, proportion of subjects who achieve any new motor milestone at Month 15

Analysis Method	Final Analysis - Population: further notes
Main analysis	
Logistic regression adjusting for each subject's age at screening and baseline number of motor milestones. Subjects who i) terminate the study prior to the 15-month assessment due to treatment failure or death OR ii) for whom it cannot be confirmed they can still maintain the baseline milestone at Month 15 will be considered as a non-responders	ITT; impute missing 15-month values per Section 5.6.2
Sensitivity analyses	
Logistic regression adjusting for each subject's age at screening and baseline number of motor milestones. Subjects who i) terminate the study prior to the 15-month assessment due to treatment failure or death OR ii) for whom it cannot be confirmed they can still maintain the baseline milestone at Month 15 will be considered as a non-responders	PPS; impute missing 15-month values per Section 5.6.2
Logistic regression adjusting for each subject's age at screening and baseline number of milestones. Subjects missing <= 5, Month 15 milestones then impute each missing milestone as 'Not, Inability'. Subjects who are i) missing all six assessments of motor milestones at Month 15 OR ( ii ) do not maintain the baseline milestone at Month 15 will be considered as a non-responders.	ITT
Logistic regression adjusting for each subject's age at screening and baseline	ITT: subjects with missing Month 15 not deemed due

number of milestones. Subjects missing <= 5, Month 15 milestones then impute each missing milestone as 'Not, Inability'. Subjects who are i) missing all six assessments of motor milestones at Month 15 OR ii) do not maintain the baseline milestone at Month 15 will be considered as a non-responders	to treatment failure or death are excluded.
Logistic regression adjusting for each subject's age at screening and baseline number of motor milestones. Responder defined as at least one new milestone compared to baseline and maintained baseline milestones.	ITT, with non-missing 15-month values

### 5.6.3 Number of new motor milestones achieved per subject at 15 months

#### 5.6.3.1 Final analysis

##### *Main analysis*

The main analysis is to compare the total number of new motor milestones achieved at 15 months between the two treatment groups, based on the ITT Set. Missing data will be handled as described in Section 5.6.2. and a total score for each visit calculated by summing the six milestones.

For each milestone the Month 15 and baseline values will be compared and if the subject can achieve a new milestone compared to baseline then it will be counted +1, if the subject is unable to achieve the milestone then it will be scored -1 and if the milestone has been maintained then it will be scored 0. These scores will then be summed to give a total score which could range between -6 (if a subject was able to perform all milestones at baseline but lost the ability and could not perform any milestones at Month 15) and + 6 (if a subject was unable to achieve any milestones at baseline but could achieve all at Month 15).

The total number of new milestones achieved by each subject at Month 15 will be compared between treatment groups by analysis of covariance with treatment group as the factor and subject age at screening and baseline number of milestones as covariates.

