#### **10.1.2 *Secondary Efficacy Endpoints***

- Proportion of subjects who achieve a 3-point or greater increase from baseline in Hammersmith Functional Motor Scale – Expanded (HFMSE) score at 15 months
- Proportion of subjects that achieve any new motor milestone at 15 months
- Number of motor milestones achieved per subject at 15 months
- Change from baseline in Upper Limb Module Test at 15 months
- Proportion of subjects that achieve standing alone at 15 months
- Proportion of subjects that achieve walking with assistance at 15 months

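### The scoring sentence for the number of new motor milestones does not limit −1 to milestones lost, so read literally each gain counts two points and an unchanged child scores below zero

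*SAP*

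**What the plan says.** Protocol 10.1.2 lists as the third secondary endpoint "Number of motor milestones achieved per subject at 15 months". The SAP keeps it third in the ordered sequence tested at 0.05 (SAP 5.2) and defines its main analysis in 5.6.3.1.

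That section first forms a total at each visit by adding the six milestones. It then says that "For each milestone the Month 15 and baseline values will be compared" and gives three rules:

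- a gain since baseline counts +1;
- a negative score is given "if the subject is unable to achieve the milestone then it will be scored -1";
- a neutral score is given "if the milestone has been maintained then it will be scored 0".

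The range is set out next: "These scores will then be summed to give a total score which could range between -6", with +6 at the other end. The lower end is explained as the case "if a subject was able to perform all milestones at baseline but lost the ability and could not perform any milestones at Month 15"; the upper end is a child with none at baseline and all six at Month 15. The score is analysed by ANCOVA with treatment as the factor and age at screening and baseline number of milestones as covariates.

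The second sensitivity analysis gives children who leave before Month 15 the worse of their last observation and zero, where zero stands for no new milestones.

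**The concern.** The three clauses do not cleanly cover the four possible states of a milestone. One that is absent at baseline and still absent at Month 15 is not new and has not been maintained. The only clause that it meets is the one for being unable, which gives −1.

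This is not a rare state. SAP 5.6.2 expects walking alone to be absent in every child at baseline, so any child who does not gain it falls into the gap.

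A programmer who follows the sentence exactly would report negative scores for children who lost nothing, and a treatment difference that cannot be read as a number of milestones. The same scale would carry into the subgroup results in SAP 5.8, where estimates are shown without tests. The endpoint also stands ahead of the Upper Limb Module, standing alone and walking with assistance in the test sequence, so its derivation should not be open to two readings.

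**Working it through.** **Inputs.** Six yes/no milestones (SAP 5.6.2); the three scoring clauses and the ANCOVA covariates (SAP 5.6.3.1); 84 and 42 subjects (SAP 5.1) for the illustration only.

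**1. The plan's own figure.** All 64 × 64 = 4096 baseline and Month 15 patterns were enumerated. The stated range of −6 to +6 is reproduced under both readings, so a range check would not expose the problem. The readings differ in how −6 arises. Literally, 64 patterns give it: every baseline pattern followed by no milestones at Month 15. Under net change only one does, the pattern that the SAP describes.

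**2. The four states.**

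| Baseline | Month 15 | Clause met | Literal | Net change |
|---|---|---|---|---|
| No | Yes | new | +1 | +1 |
| Yes | No | unable | −1 | −1 |
| Yes | Yes | maintained | 0 | 0 |
| No | No | unable only | −1 | 0 |

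**3. The total score.** Let B be the number present at baseline, N the number gained and L the number lost. The number not done at Month 15 is 6 − (B + N − L).

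- Literal: N − [6 − (B + N − L)] = 2N − L + B − 6.
- Net change: N − L.

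Both identities held for all 4096 patterns. Examples:

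| Child | Literal | Net change |
|---|---|---|
| B = 1, no change | 0 − 0 + 1 − 6 = −5 | 0 |
| B = 1, one gain | 2 − 0 + 1 − 6 = −3 | +1 |
| B = 1, two gains | 4 − 0 + 1 − 6 = −1 | +2 |
| B = 1, sitting lost | 0 − 1 + 1 − 6 = −6 | −1 |
| B = 2, no change | 0 − 0 + 2 − 6 = −4 | 0 |
| B = 5, no change | 0 − 0 + 5 − 6 = −1 | 0 |

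**4. What the ANCOVA does with it.** Rewrite the literal score as 2(N − L) + L + (B − 6). The last term is linear in the baseline count, which is a covariate, so the intercept and that covariate absorb it exactly. The literal treatment difference is therefore twice the net-change difference plus the adjusted difference in losses.

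- No losses: the estimate and its standard error are exactly doubled, and p is identical.
- Some losses: gains weigh 2:1 against losses, and p can move.

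One simulated data set for each case (84:42) illustrates this. The documents give no gain or loss rates, so all rates are assumptions: sitting present in all at baseline, walking alone in none, 12% for each of the other four; a 6% chance of gaining each absent milestone on active and 2% on sham.

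| Assumed loss per milestone held | Literal difference (SE), p | Net-change difference (SE), p |
|---|---|---|
| none | 0.2196 (0.1602), 0.173 | 0.1098 (0.0801), 0.173 |
| 15% sham, 8% active | 0.7534 (0.2080), 0.00043 | 0.4356 (0.1238), 0.00061 |

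**5. Zero in the sensitivity analysis.** Under net change, taking the worse of the last observation and zero removes any net gain in a child who left early. Under the literal score, a child with sitting only and no losses exceeds zero only from three gains (2 × 3 + 1 − 6 = +1; two gains give −1). The cap would then rarely act, and zero would not mean no new milestones.

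**The case against.** The strongest reply is that the section already settles its meaning. The comparison with baseline governs all three clauses; the lowest score is explained by lost ability; the visit total changes by gains minus losses; zero is the neutral value in the sensitivity analysis; and SAP 5.6.8 plans a display of the change in total milestones. All of this fits +1 for a gain, −1 for a loss and 0 otherwise. It stands as evidence of intent. A reader might infer from the sentence that the SAP means to penalise milestones that a child never had; the documents do not support that.

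It does not remove the defect. The example describes an extreme and never scores the absent/absent case. Nor can that case be brought under the maintained clause: SAP 5.6.2.1 uses that word for milestones already achieved at baseline.

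Three further limits stand. The −5 applies only where sitting is the sole baseline milestone. The offset does not reach the treatment comparison. And it would be tempting to say that −6 to +6 cannot occur, because "subjects would be expected to all have achieved and maintained at baseline the milestone" of sitting, so that sitting cannot be gained, while walking alone is expected in none and cannot be lost, leaving −5 to +5. SAP 5.6.2 states an expectation only. SAP section 3 foresees subjects who cannot sit and excludes them from the Per-protocol Set, but they remain in the ITT Set, on which this analysis is run. The stated range is the arithmetic range of six items and is correct.

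**Conclusion.** The concern holds as a wording defect in the derivation of an endpoint under formal testing. The sentence, followed exactly, gives 2N − L + B − 6, whereas the rest of the section requires N − L.

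The consequence is confined mainly to the arm means, the treatment difference and its confidence interval. The difference and standard error are exactly doubled when nobody loses a milestone. When some do, no single inflation factor can be given, because it depends on loss rates that the documents do not state. The literal rule also largely disables the zero cap in one sensitivity analysis.

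A reader might infer that the ordered testing, or its error control, is compromised. The algebra does not support that: without losses p is the same under both readings, and with losses the shift in the one illustration was small (0.00061 against 0.00043, on assumed rates). The point is worth correcting, but it does not threaten the trial's conclusions.

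**What to change.** Replace the scoring sentence in SAP 5.6.3.1 with: No at baseline and Yes at Month 15 = +1; Yes at baseline and No at Month 15 = −1; unchanged status (Yes/Yes or No/No) = 0. Add that the sum equals the Month 15 total minus the baseline total, which ties it to the visit total already defined there. Keep the stated range of −6 to +6.

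The cost is one sentence of SAP text, best made before unblinding. It needs no new data and no change to the model or the test sequence.

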##### *Sensitivity analysis*

Three sensitivity analyses will be performed. In the first, the analysis described above will be performed on the PPS. In the second, the same analysis will be repeated in the ITT, with an exception to assign the worst of last available observation and zero (0) new motor milestones achieved for subjects who terminate the study prior to the 15-month assessment the study prior to the 15-month assessment. In the third sensitivity analysis, only the subset of subjects in the ITT Set who have non-missing values for all six milestones at 15 months will be analyzed.

### 5.6.3.2 Summary of analyses

#### Summary of analyses for the secondary endpoint, Number of motor milestones achieved per subject at 15 months

Analysis Method	Final Analysis - Population: further notes
Main analysis	
Analysis of covariance (treatment as fixed effect) with subject's age at screening and baseline value as covariates	ITT, impute missing 15-month values per Section 5.6.2
Sensitivity analyses	
Analysis of covariance (treatment as fixed effect) with subject's age at screening and baseline value as covariates	PPS, impute missing 15-month values per Section 5.6.2
Analysis of covariance (treatment as fixed effect) with subject's age at screening and baseline value as covariates	ITT, impute worst of last available observation and zero (0) new motor milestones achieved for subjects who discontinue prior to Month 15
Analysis of covariance (treatment as fixed effect) with subject's age at screening and baseline value as covariates	ITT, with non-missing 15-month values

